12.4.7 Safety Variables

Safety measures will be analyzed using the safety population. Medical Dictionary for Regulatory Activities (MedDRA) nomenclature will be used to code adverse events. Incidence rates of each treatment-emergent adverse event will be summarized by primary system organ class and preferred term. Summary tables will be generated for all treatment-emergent adverse events regardless of causality as well as for those considered to be treatment-related.

12.4.8 Planned Interim Analyses

An interim analysis will be performed when the last enrolled patient in Stage 1 completes Month 3 of the Expansion Cohort. There is no plan to stop the study for efficacy on the basis of the interim analysis. However, termination in individual dose groups due to safety, tolerability and/or futility may occur. Statistical significance will not be declared at the time of the interim analysis.

A final database lock will occur at the completion of Stage 2 and the safety, tolerability, and efficacy data from both Stage 1 and 2 will be analyzed separately and in a combined fashion to fully leverage the advantage of this two-stage study design. At the final analysis, statistical significance will be declared for two-sided p-values < 0.05.

Given the exploratory nature of the study no adjustments for multiplicity will be applied across the primary or secondary endpoints.

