12.1 Sample Size Determination

The sample size is determined empirically. Xiidra achieved a 0.25 unit difference between lifitegrast ophthalmic solution and vehicle in mean change from baseline to day 84 in inferior cornel staining and a standard deviation of approximately 0.75 in Phase 2. Sample sizes for this study are based on detecting a 0.35 unit difference between the active and vehicle groups, assuming a standard deviation of 0.75. In Stage 1 the number of expected enrolled subjects varies between 43 and 53 subjects in the active group and between 37 and 47 subjects in the vehicle group. In Stage 2 the number of expected enrolled subjects is 60 in the active group and 30 to 60 subjects in the vehicle group. Thus, the combined sample provides between 103 and 113 subjects in the active group and between 67 and 77 subjects in the matching vehicle group or between 97 and 107 subjects in the combined vehicle group. Under these assumptions and allowing a dropout rate of 10%, sample sizes of 93 in the active treatment group and 60 in the vehicle group will yield 80% power to show a significant difference at the $\alpha = 0.05$ level using a two-sample t-test.

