8.4 Data Analysis Conventions

All data analysis will be performed by Statistics & Data Corporation (SDC) after the study is completed and the database has been locked and released for unmasking. Statistical programming and analyses will be performed using SAS® Version 9.4 or higher. Output will be provided in rich text format (RTF) for tables and portable document format (PDF) for tables, listings, and figures using landscape orientation. All study data will be listed by subject, treatment, and visit (as applicable) based on all randomized subjects unless otherwise specified.

Summaries for continuous and ordinal variables will include the number of observations (n), arithmetic mean, standard deviation (SD), median, minimum, and maximum). Minima and maxima will be reported with the same precision as the raw values; means and medians will be presented to one additional decimal place than reported in the raw values. SDs will be presented to two additional decimal places than reported in the raw values. Summaries for discrete variables will include frequency counts and percentages. All percentages will be rounded to one decimal place (i.e., XX.X%). Differences between active treatment groups and vehicle will be calculated as Active minus Vehicle and change from baseline will be calculated as follow-up visit minus baseline. The baseline measure will be defined as the last non-missing measure prior to initiation of investigational treatment.

Statistical comparisons between each AXR-159 Ophthalmic Solution group will be to the vehicle group at matched dosing frequency (TID or BID). AXR-159 Ophthalmic Solution plus Artificial Tear group will be compared to both AXR-159 Ophthalmic Solution and to the vehicle group at matched dosing frequency.

A final database lock will occur at the completion of Stage 2 and the safety, tolerability, and efficacy data from both Stage 1 and 2 will be analyzed separately and in a combined fashion to fully leverage the advantage of this two-stage study design.

All statistical tests will be two-sided with a significance level of 0.05 ($\alpha = 0.05$) unless otherwise specified. Confidence intervals (CI) for differences between treatment groups will be two-sided at 95% confidence. All p-values will be rounded to four decimal places; p-values less than 0.0001 will be presented as “<0.0001”; p-values greater than 0.9999 will be presented as “>0.9999”.

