The primary analysis will be performed on the mITT population with the LOCF imputation method for missing values. For the LOCF analysis, the last value from the previous visits will be carried forward. Only pre-CAE® or non-CAE® time points will be used to impute a missing pre-CAE® value.

As sensitivity analyses, the primary analysis will also be performed on the mITT2 population with LOCF, the PP population with LOCF, the mITT population with observed data only, and the mITT population with MCMC imputation.

The MCMC method will be performed using the SAS procedure PROC MI. The SAS code for obtaining multiple imputation data is:

```

PROC MI DATA = INDATA SEED = SEED_VALUE OUT = OUTDATA NIMPUTE = 20
   MINIMUM = 0 MAXIMUM = 4 ROUND = 0.5;
   BY TREATMENT
   MCMC INITIAL = EM;
   VAR BASELINE_ICSS ICSS;
RUN;

```

where

- *INDATA* is the name of the input dataset
- *OUTDATA* is the name of the output dataset

- *TREATMENT* is the name of the treatment group variable
- *BASELINE_ICSS* is the baseline pre-CAE® inferior fluorescein staining score in the study eye
- *ICSS* is the pre-CAE® inferior fluorescein staining in the study eye at Visit 5 (Day 85 ± 2)

In the above, the random number seed *SEED_VALUE* will be set to 62521 + S, where S = 1 for Stage 1 data analysis, S = 2 for Stage 2 data analysis, and S = 3 for analysis of the combined Stage 1 and Stage 2 data.

After obtaining twenty complete data sets and calculating changes from baseline, the following SAS code will be used to run the ANCOVA model on each data set and combine the results from the twenty analyses:

```

PROC MIXED DATA = OUTDATA;
  BY _IMPUTATION_;
  CLASS TREATMENT;
  MODEL CHANGE_ICSS = BASELINE_ICSS BASELINE_EDS TREATMENT
    / SOLUTION COVB;
  LSMEANS TREATMENT / CL PDIFF;
  ODS OUTPUT LSMEANS = OUTLS DIFFS = OUTDIFFS;
RUN;
PROC SORT DATA=OUTLS; BY TREATMENT _IMPUTATION_; RUN;
PROC MIANALYZE DATA=OUTLS;
  BY TREATMENT;
  MODELEFFECTS ESTIMATE;
  STDERR STDERR;
RUN;

DATA OUTDIFFS;
  SET OUTDIFFS;
  COMPARISON = TREATMENT||' - '||LEFT(_TREATMENT);
RUN;
PROC SORT DATA=OUTDIFFS; BY COMPARISON _IMPUTATION_; RUN;
PROC MIANALYZE DATA=OUTDIFFS;
  BY COMPARISON;
  MODELEFFECTS ESTIMATE;
  STDERR STDERR;
RUN;

```

where

- *TREATMENT* is the name of the treatment group variable
- *BASELINE_ICSS* is the baseline pre-CAE® inferior fluorescein staining score in the study eye
- *BASELINE_EDS* is the baseline pre-CAE® eye dryness score

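### For the regimen carried from Stage 1 into Stage 2, each primary endpoint is tested on three data sets at 0.05, and neither document says which one decides

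*Protocol*

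**What the plan says.** Protocol 12.4.8, repeated in SAP 8.4, states that "efficacy data from both Stage 1 and 2 will be analyzed separately and in a combined fashion to fully leverage the advantage" of the design. The next sentence of the protocol reads: "At the final analysis, statistical significance will be declared for two-sided p-values < 0.05". SAP 8.4 applies the same level throughout: "All statistical tests will be two-sided with a significance level of 0.05". Neither sentence names a data set.

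The SAP carries out all three analyses. Section 20 lists Stage 1, Stage 2 and combined tables for every primary endpoint, and the imputation seeds in 13.1.1 to 13.1.5 run over three data sets, ending with "S = 3 for analysis of the combined Stage 1 and Stage 2 data". The null and alternative hypotheses (Protocol 12.3, SAP 2.5) mention no stage.

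Two parts of the protocol point in different directions:

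- Section 12.1 bases its power on the pooled sample: "Thus, the combined sample provides between 103 and 113 subjects in the active group", with 67 to 77 on matching vehicle.
- Section 5 asks Stage 1 only for an early efficacy signal and places the hypothesis of superiority over vehicle under Stage 2.

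Multiplicity adjustment is waived for treatment groups and primary endpoints (Protocol 12.4.4, SAP 8.5), for secondary endpoints (Protocol 12.4.8) and for the Stage 1 interim look (SAP 17). SAP 8.5 calls all efficacy analyses exploratory. No waiver mentions the choice among final data sets.

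**The concern.** A reader of the final report will want to know whether the carried-forward regimen beat vehicle on, say, inferior corneal staining. The plan will produce three p-values for that question and one significance rule that fits them all. If they fall on different sides of 0.05, the answer depends on a choice made after unmasking.

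Two things are at stake. The chance of a nominal claim for an inactive drug exceeds the stated 0.05. And if the drug works as planned, a split between Stage 2 alone and the combined data is a common result that the plan should already know how to read.

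**Working it through.** **Inputs (Protocol 12.1, same text in SAP 5).** The design is for "detecting a 0.35 unit difference between the active and vehicle groups, assuming a standard deviation of 0.75". The sensitivity value comes from "Xiidra achieved a 0.25 unit difference between lifitegrast ophthalmic solution and vehicle". For Stage 1 sizes: "In Stage 1 the number of expected enrolled subjects varies between 43 and 53 subjects in the active group and between 37 and 47" on vehicle. Stage 2 has 60 active and 30 to 60 vehicle subjects, and dropout is 10%. The matching-vehicle totals imply 30 in Stage 2 (37 + 30 = 67, 47 + 30 = 77) and the combined-vehicle totals imply 60 (37 + 60 = 97, 47 + 60 = 107). Both ends are shown.

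**The plan's own figure.** 103 × 0.9 = 92.7 and 67 × 0.9 = 60.3, hence 93 and 60. The standardised effect is 0.35 / (0.75 × √(1/93 + 1/60)) = 2.818, and Φ(2.818 − 1.96) = 0.805; the exact noncentral t gives 0.7996. The stated 80% is reproduced, and it belongs to the combined data set at its smallest size.

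**Stage 2 alone, after dropout.** With 54/27: 0.35 / (0.75 × √(1/54 + 1/27)) = 1.980, and Φ(0.020) = 0.51. With 54/54: 2.425, and Φ(0.465) = 0.68.

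**Joint behaviour.** The Stage 2 subjects are part of the combined sample, so the two test statistics are correlated:

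r = √[(1/n_A + 1/n_V for combined) / (1/n_A + 1/n_V for Stage 2)]

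For 39/33 + 54/27, r = √[(1/93 + 1/60) / (1/54 + 1/27)] = √(0.0274/0.0556) = 0.70. For 48/42 + 54/27, r = 0.66. With 54/54 in Stage 2, r is 0.78 and 0.74.

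Simulating arm means (two million trials per row, known SD 0.75, tests at |z| > 1.96) gives:

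| Evaluable, Stage 1 + Stage 2 | False positive: Stage 2 or combined | False positive: any of three | Stage 2 significant at 0.35 | Combined significant at 0.35 | Differ at 0.35 | Differ at 0.25 | Differ, no effect |
|---|---|---|---|---|---|---|---|
| 39/33 + 54/27 | 8.3% | 11.5% | 51% | 80% | 34% | 31% | 6.6% |
| 48/42 + 54/27 | 8.5% | 11.5% | 51% | 85% | 37% | 35% | 7.0% |
| 39/33 + 54/54 | 8.0% | 11.5% | 68% | 88% | 23% | 27% | 6.0% |
| 48/42 + 54/54 | 8.1% | 11.5% | 68% | 91% | 25% | 31% | 6.3% |

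The last three columns give how often Stage 2 and combined fall on different sides of 0.05. A consistency check for no effect: the two tests differ at a rate of 2 × 8.5% − 10% = 7.0%, as tabulated.

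**Direction of the split.** At 0.35 with 54/27, the combined test alone is significant in 32-36% of trials and Stage 2 alone in about 2%. With 54/54 the figures are 22-24% and 1-1.5%.

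**The combined model.** SAP 13.1.1 gives ANCOVA code for each stage and no stage term for the combined fit, although the combined CMH analyses (SAP 13.2) stratify by Stage. Allocation differs by stage. In the smallest sample, Stage 2 supplies 54/93 = 58% of active but 27/60 = 45% of vehicle subjects. A shift m in mean change between stages, if not absorbed by the baseline covariates, would move an unadjusted combined contrast by 0.13m. Adding Stage costs little. The information is 39×33/72 + 54×27/81 = 35.9 against 93×60/153 = 36.5, and the power is Φ(0.35/0.75 × √35.9 − 1.96) = 0.80.

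**The case against.** The strongest reply is that this is an openly exploratory Phase 2 study. It tests five primary variables in several regimens, each at 0.05, and waives adjustment, so going from 5% to about 8% for one regimen adds little. That is fair about weight. But no alpha adjustment is being asked for, and the exploratory label does not say which result answers the hypothesis when the combined p-value is below 0.05 and the Stage 2 one is not. The plan itself declares significance at 0.05.

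A second reply is that the power text makes the combined analysis the obvious choice. It probably is, but that remains an inference, and section 5 of the protocol points to Stage 2. Marking some tables for topline delivery (SAP 20) governs reporting, not decision.

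Four stronger readings that a reader might infer are not supported:

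- *Every primary hypothesis is tested three times in every regimen.* Stage 1 expands a single regimen. Regimens first used in Stage 2 have no Stage 1 active data to pool.
- *The data sets would contradict each other.* Nearly all splits are a significant combined test beside a smaller Stage 2 test that misses 0.05. With no effect, the tests differ in only 6-7% of trials.
- *Stage 1 is an equal candidate, so 11.5% is the main figure.* Section 5 gives Stage 1 a lesser role, and significance may not be declared at the interim. Nothing bars a Stage 1 claim at the final lock, but it is the least plausible deciding analysis.
- *A promised error rate is breached.* The documents promise no control beyond the level of each test.

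The rates also count both directions. In the drug-favouring direction, 8.5% becomes 8.5/2 = 4.3% against a nominal 2.5%.

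**Conclusion.** The point holds for the one regimen expanded in Stage 1 and continued in Stage 2, and it should be fixed. The deciding data set is unnamed, and the existing waivers do not cover the choice. The main figures are a two-sided false-positive rate of about 8% per endpoint (8.0-8.5%) if Stage 2 or combined may count, and, at the planned effect, a split between them in roughly one trial in three with 30 Stage 2 vehicle subjects or one in four with 60.

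These figures assume the same effect and SD in both stages, normal means, 10% dropout, and no conditioning on the Data Review Committee's review of Stage 1. That review would change them. As an illustration, if the regimen stopped whenever the Stage 1 estimate pointed against the drug, and a stopped regimen counted as no claim, symmetry halves the 8.5% to 4.3%. The exploratory status lowers the consequence but does not fill the gap.

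**What to change.** Add to Protocol 12.4.8 and SAP 8.4 and 13.1:

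- For the regimen expanded in Stage 1 and continued in Stage 2, the combined comparison with matched vehicle decides, because the 80% power was calculated on it. Stage enters the combined ANCOVA as a factor, as the SAP already does for the combined CMH analyses.
- For regimens first studied in Stage 2, the Stage 2 comparison with concurrent matched vehicle decides.
- All other data-set tables are supportive, and their p-values are footnoted as nominal.

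The cost is a few sentences, one extra model term with its code in SAP 13.1, and table footnotes. No subjects or visits are added, and power stays at about 80%. The sponsor gives up the option of citing whichever data set turns out significant. The change should be made before unmasked data are available, since it would carry little credibility afterwards.

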12.4.9 Sub-Group Analyses

Patients will be stratified by the Pre-CAE® inferior corneal staining score (ICCS) (i.e., ≤ 1.5 or > 1.5) according to the Ora Calibra® staining scale and eye dryness score (i.e., < 60 or ≥ 60) in the study eye.

Subgroup analyses are planned for the 4 groups defined by the 2 stratification factors (Pre-CAE®):

1. inferior corneal staining score (ICCS) ≤ 1.5 according to the Ora Calibra® staining scale and eye dryness score < 60
2. inferior corneal staining score (ICCS) ≤ 1.5 according to the Ora Calibra® staining scale and eye dryness score ≥ 60
3. inferior corneal staining score (ICCS) > 1.5 according to the Ora Calibra® staining scale and eye dryness score < 60
4. inferior corneal staining score (ICCS) > 1.5 according to the Ora Calibra® staining scale and eye dryness score ≥ 60.

12.4.10 Tabulation of Individual Participant Data

Individual participant data will be listed by measure and time point.

12.4.11 Exploratory Analyses

The statistical analysis plan (SAP) will provide a detailed description of the planned exploratory statistical analysis.

12.4.12 Pharmacokinetics Analyses

A model independent approach will be used to calculate the pharmacokinetic parameters of AXR-159 in blood. Pharmacokinetic parameters for blood will only be calculated for samples collected from patients who receive study treatment (Stage 1, the first 40 patients in the expansion cohort). To enable only bioanalysis of samples from patients who receive active AXR-159 treatment, the randomization codes will be made available based

on AxeroVision Inc. internal procedures. Pharmacokinetic parameters including area under the curve from time 0 to t (AUC_{0-t}), AUC from time 0 to infinity ($AUC_{0-\infty}$), C_{max} , time to highest observed concentration (T_{max}), and half-life ($T_{1/2}$) will be calculated when possible.

The concentration of AXR-159 in blood and tear samples will be summarized by dose and timepoint using descriptive statistics, if applicable.

13 COMPLIANCE WITH GOOD CLINICAL PRACTICES, ETHICAL CONSIDERATIONS, AND ADMINISTRATIVE ISSUES

This study will be conducted in compliance with the protocol, current Good Clinical Practices (GCPs), including the International Conference on Harmonisation (ICH) Guidelines, and in general, consistent with the Declaration of Helsinki. In addition, all applicable local, state, and federal requirements relevant to the use of IP in the countries involved will be adhered to.

13.1 Protection of Human Subjects

13.1.1 Subject Informed Consent

Informed consent/assent must take place before any study specific procedures are initiated. Signed and dated written informed consent must be obtained from each subject and/or from the subject's parent or legal guardian prior to enrollment into the study. If the subject is under the legal age of consent, the consent form must be signed by a legal guardian or as required by state and/or local laws and regulations.

All informed consent/assent forms must be approved for use by the sponsor and receive approval/favorable opinion from an IRB/IEC prior to their use. If the consent form requires revision (e.g., due to a protocol amendment or significant new safety information), it is the investigator's responsibility to ensure that the amended informed consent is reviewed and approved by Ora prior to submission to the governing IRB/IEC and that it is read, signed and dated by all subjects subsequently enrolled in the study as well as those currently enrolled in the study.

If informed consent is taken under special circumstances (oral informed consent), then the procedures to be followed must be determined by Ora and/or sponsor and provided in writing by Ora and/or sponsor prior to the consent process.

13.1.2 Institutional Review Board (IRB) Approval

This study is to be conducted in accordance with IRB regulations (U.S. 21 CFR Part 56.103). The investigator must obtain appropriate IRB approval before initiating the study and re-approval at least annually.

Only an IRB/IEC approved version of the informed consent form will be used.

13.2 Ethical Conduct of the Study

This study will be conducted in accordance with the ethical principles that originated with the Declaration of Helsinki.

13.3 Subject Confidentiality

All personal study subject data collected and processed for the purposes of this study should be maintained by the investigator and his/her staff with adequate precautions as to ensure that the confidentiality of the data is in accordance with local, state, and federal laws and regulations.

Monitors, auditors and other authorized representatives of Ora, the sponsor, the IRB/IEC approving this study, the FDA, the DHHS, other domestic government agencies, and other foreign regulatory agencies will be granted direct access to the subject's original medical and study records for verification of the data and/or clinical trial procedures. Access to this information will be permitted to the aforementioned individuals to the extent permitted by law.

A report of the results of this study may be published or sent to the appropriate health authorities in any country in which the IP may ultimately be marketed, but the subject's identity will not be disclosed in these documents.

13.4 Documentation

Source documents may include a subject's medical records, hospital charts, clinic charts, the investigator's study subject files, as well as the results of diagnostic tests such as X-rays, laboratory tests, and EKGs. The investigator's copy of the CRFs serves as the investigator's record of a subject's study-related data.

13.4.1 Retention of Documentation

All study related correspondence, subject records, consent forms, record of the distribution and use of all IP, and copies of CRFs should be maintained on file for at least two years after the last approval of a marketing application in an ICH region and until there are no pending or contemplated marketing applications in an ICH region; or until at least two years have elapsed since the formal discontinuation of clinical development of the IP. These documents will be retained for a longer period if required by the applicable regulatory requirements or by an agreement with the sponsor. It is the responsibility of the sponsor to inform the investigator/institution as to when these documents no longer need to be retained.

If the responsible investigator retires, relocates, or for other reasons withdraws from the responsibility of keeping study records, custody must be transferred to a person who will accept the responsibility. The sponsor must be notified in writing of the name and address of the new custodian.

13.5 Labeling, Packaging, Storage, Accountability, and Return or Disposal of Investigational Product

13.5.1 Labeling/Packaging

Each vial is embossed with lot-specific information on the vial tab. The vials are produced as a card of five (5) vials with each card being packaged in hermetically sealed aluminum foil pouches containing an identifying label on the pouch exterior. Ten (10) pouched cards are further packaged into a paper board carton comprising a two week supply of drug product. The carton has an identifying label with lot-specific information on its exterior.

13.5.2 Storage of Investigational Product

The IP must be stored at refrigerated temperature (2-8 °C) in its original packaged kit until dispensed to the patient in a secure area accessible only to the investigator and his/her designees. The IP will be administered only to subjects entered into the clinical study, in accordance with the conditions specified in this protocol.

